

• Age <math>\geq 18</math> years

• Body mass index (BMI) <math>\geq 30 \text{ kg/m}^2</math>

• Own a smartphone (Apple iOS or Android OS)

• Baseline eating period <math>\geq 14</math> hours/day

• If patients are on cardiovascular medications (HMG CoA reductase inhibitors (statins), other lipid modifying drugs (including over the counter drugs such as red yeast rice and fish oil), anti-hypertensives), no dose adjustments will be allowed during the study period

	

• Anti-diabetic medications or insulin within the last 6 months

• Manifest diabetes, defined as fasting glucose <math>\geq 126 \text{ mg/dL}</math>, HbA1c <math>\geq 6.5\%</math>, or diagnosis of diabetes

• Currently taking any medication that is meant for, or has known effect on, appetite or body weight.

• Pregnant or breast-feeding

• Caregiver for a dependent requiring frequent nocturnal care/sleep interruptions. Shift workers with variable (e.g. nocturnal) hours

• Prolonged international travel (time zone changes) during the study period

• Taking therapeutic anticoagulation which might increase risk of bleeding from fat biopsy

• History of surgical intervention for weight loss

• Currently enrolled in a weight-loss or weight-management program

• On a special or prescribed diet for other reasons (e.g. Celiac disease)

• Known inflammatory and/or rheumatologic disease

• Active tobacco abuse or illicit drug use or history of treatment for alcohol abuse

• History of bone marrow or solid organ transplant

• History of heart failure

• History of major adverse cardiovascular events (acute coronary syndrome (ACS), percutaneous coronary intervention, coronary artery bypass graft surgery, stroke/transient ischemic attack (TIA)).

• History of atrial fibrillation or atrial flutter

• History of malignancy, other than non-melanoma skin cancer, that is currently being treated, or that has not been treated with definitive therapy and considered to be in remission.

• History of hypo- or hyperthyroidism requiring dose titration of thyroid replacement medication(s) within the past 3 months (i.e. hypothyroidism on a stable dose of thyroid replacement therapy is not an exclusion)

• History of adrenal disease

• History of eating disorder

• History of cirrhosis

• History of stage 4 or 5 chronic kidney disease or requiring dialysis

• History of HIV/AIDS

• Uncontrolled psychiatric disorder (including history of hospitalization for psychiatric illness).

• History of obstructive sleep apnea (not on stable positive pressure therapy or other treatment for at least 3 months prior to enrollment)

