11. Inability to start lipid-lowering, anti-hypertensive, and anti-diabetics medications or undergo dose adjustments of these medications during the study period: potential risk of incompletely controlled lipid, blood pressure, and/or blood sugar values during the study period which could have either acute (e.g. symptomatic high or low blood pressure, symptomatic high or low blood sugars) and/or long-term risks (e.g. potential contribution to long-term risk of cardiovascular events). However, if any of the monitored parameters during this study become abnormal to the point of necessitating immediate treatment based on the judgement of the investigators or participant's primary physician or cardiologist, the participant will be advised to immediately stop the study and seek medical attention.
12. Unscheduled visits: There may be the possibility of having subjects return for unscheduled visits in between the scheduled visits. This would be for the following reasons: PI discretion, if the bloodwork needs to be redrawn due to lab or processing errors, repeat adipose tissue biopsy because of inadequate or uninterpretable sample, and/or reapplication of the continuous glucose monitor and/or actigraphy watch if it fell off or did not record data. Participants will not be given additional compensation for unscheduled visits.
13. A potential loss of confidentiality: The UCSD Institutional Review Board (IRB), the FDA, and other government agencies may inspect the study records. To minimize the risk of a potential loss of confidentiality, subjects will be assigned a unique subject code and their blood samples will be assigned a different unique specimen code. A separate paper document will link patient identifiers with subject codes and specimen codes. This document will be kept in a secure location in a locked cabinet. Only the PI and study coordinator will have the key to the cabinet. No research documents will have any patient identifiers and will only be labeled with the unique assigned subject codes.

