#### AE Management

1. Blood Draw:
  - a. Prior to enrollment into the study, the patient will be educated on the risks of the blood draw. The phlebotomist will calm the patient beforehand to reduce anxiety/fear and minimize the probability of vasovagal response. Only sterile needles and gauze will be used to prevent allergic reactions and infection. The area of the blood draw will be thoroughly sanitized with an alcohol wipe prior to the needle stick. Care will be used when penetrating the skin with the needle so that there is a minimized risk of punctured artery and damaged nerve. The needle stick will be done swiftly and securely by an experienced phlebotomist in order to reduce pain. Pressure will be applied on the area immediately after the needle stick to minimize the risk of hematoma. The phlebotomist will inform the patient on when and how to undress their puncture site. [name], who is a cardiologist, will be overseeing the procedure to check for the patient's vital signs. [name] phone number will be given to the patient for any questions or concerns that may arise in the future.
  - b. In the event of an AE that occurs during the appointment, the facility (CTRI) is equipped with trained medical staff (physicians and nurses) who can respond quickly. Should an event occur, [name] and the nurses will be nearby to administer immediate medical care and send the patient to the nearest hospital. If the AE occurs after the appointment, the patient will be referred for prompt medical attention. The patient will be withdrawn from the study. [name] will monitor the patient until the problem has been resolved or has stabilized.
2. Actigraphy device:
  - a. If participants develop skin irritation, they will be asked to notify the study personnel immediately.
  - b. The instructions for use of the watch advise on the measures participants can take to limit the chance of experiencing any problems (such as tightness of wearing and regular cleaning).
3. Use of continuous glucose monitor:
  - a. Prior to enrollment into the study, the patient will be educated on the risks of wearing a continuous glucose

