monitor. To minimize risk, the continuous glucose monitor will be placed and removed only during study visits by a trained member of the study team. The device will be inserted using the following protocol: 1) Wash hands with soap and water, 2) Choose sensor insertion site, 3) Clean the skin over the insertion site with an alcohol wipe, 4) A skin adhesive product may or may not be used, 5) The sensor delivery device will then be used to position the sensor under the participant's skin. In the event of bleeding at the insertion site, the patient will be advised to hold pressure over the area and present for medical evaluation. For other local site issues, such as irritation, discomfort, or redness, if these symptoms are unacceptable to the participant the study team will immediately assist the participant with removal of the device and the patient will be removed from the study and will be monitored for resolution of symptoms. Sensor or needle fracture will be addressed immediately by the study investigators with assistance from the device manufacturer.

- b. In the event of an AE that occurs during the appointment, the facility (CTRI) is equipped with trained medical staff (physicians and nurses) who can respond quickly. Should an event occur, [name] and the nurses will be nearby to administer immediate medical care and send the patient to the nearest hospital. If the AE occurs after the appointment, the patient will be referred for prompt medical attention. The patient will be withdrawn from the study. [name] will monitor the patient until the problem has been resolved or has stabilized.
4. Reduced daily feeding period (from  $\geq$  14 hours per day to 10 hours per day)
  - a. Prior to enrollment into the study, the patient will be educated on the risks of reducing the total number of hours of oral intake during a 24 hour period. The participant will be advised that hunger and/or subjective feelings of fatigue or malaise may occur. Risk of hypoglycemia will be discussed, especially in those patients with impaired fasting glucose. Participants should immediately consume sugar (e.g. candies, glucose) in the event of symptomatic hypoglycemia.
  - b. In the event of an AE, the patient will be referred for prompt medical attention and may be withdrawn from the study. [name] will monitor the patient until the problem has been resolved or has stabilized.

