5. Inability to start lipid-lowering, anti-hypertensive, and anti-diabetics medications or undergo dose adjustments of these medications during the study period
  - a. Because initiation or adjustment of lipid-lowering, anti-hypertensive, and anti-diabetes medications will confound the results of this study, these medication changes cannot occur during the study period without a participant being withdrawn from the study. Prior to enrollment, the participant will be educated on the potential risks associated with incompletely controlled lipid, blood pressure, and/or blood sugar values during the study period, including symptomatic high or low blood pressures and symptomatic high or low blood sugars. Prior to enrollment, the participant will also be educated regarding the potential contribution to long-term risk of cardiovascular disease/events associated with a 12 week study period during which medication adjustments are not allowed, however it will be noted that such long-term risks associated with this aspect of the study cannot be quantified.
  - b. In the event of an AE, the patient will be referred for prompt medical attention and will be withdrawn from the study so that medication changes can be made. [name] will monitor the patient until the problem has been resolved or has stabilized.
6. Adipose tissue biopsy:
  - a. Prior to enrollment into the study, the patient will be educated on the risks of the adipose tissue biopsy. Research staff will calm the patient beforehand to reduce anxiety/fear and minimize the probability of vasovagal response. Only sterile needles and gauze will be used to prevent allergic reactions and infection. The area of the biopsy will be thoroughly sanitized with an alcohol wipe prior to the needle stick. Care will be used when penetrating the

skin with the needle so that there is a minimized risk of punctured artery and damaged nerve. The needle stick will be done swiftly and securely by an experienced provider in order to reduce pain. Pressure will be applied on the area immediately after the needle stick to minimize the risk of bleeding and hematoma. The provider performing the biopsy will inform the patient on when and how to undress their puncture site. [name], who is a cardiologist, will be performing or overseeing the procedure. [name] phone number will be given to the patient for any questions or concerns that may arise in the future.

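### Stopping the CGM or changing a medication takes a participant out of the study, so visit 5 outcomes that could be kept at little cost are lost

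*Combined protocol and SAP*

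**What the plan says.** The withdrawal rules are in section 15, AE Management, with related text in sections 10 and 14.

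- **CGM.** When local irritation, discomfort or redness is more than the participant will accept, the rule is that staff "immediately assist the participant with removal of the device and the patient will be removed from the study".
- **Medication.** For lipid-lowering, anti-hypertensive and anti-diabetes drugs, "these medication changes cannot occur during the study period without a participant being withdrawn from the study". The stated reason is confounding. The inclusion table in section 10 sets the matching condition for cardiovascular drugs: "no dose adjustments will be allowed during the study period". Section 14, item 11 adds that if a monitored value needs immediate treatment, "the participant will be advised to immediately stop the study and seek medical attention".
- **Procedures.** The blood-draw, CGM, biopsy and DEXA entries each carry the same sentences: "If the AE occurs after the appointment, the patient will be referred for prompt medical attention. The patient will be withdrawn from the study".
- **Softer or silent entries.** For the actigraphy watch: "If participants develop skin irritation, they will be asked to notify the study personnel immediately". Section 14, item 12 provides for "reapplication of the continuous glucose monitor and/or actigraphy watch if it fell off or did not record data". For an adverse event of the reduced eating window itself, withdrawal is optional.

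After withdrawal, the plan describes medical monitoring until the problem resolves or stabilises. It does not mention outcome assessment.

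The Statistical analysis text in section 9 regresses the visit 5 level on group, with the visit 2 level as covariate, for Aims 1 to 3. Visit 5 is where the final biopsy (Aims 1 and 2), fasting blood (Aim 3) and DEXA (Exploratory Aim 1) are taken. No analysis population or missing-data method is stated. Losses are covered only by the 15% attrition allowance.

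**The concern.** The plan does not separate stopping a device or procedure, or breaking the medication restriction, from leaving the study. Someone withdrawn after randomisation and before visit 5 has no value for the main regressions.

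The CGM rule is the clearest case. The sensor serves Exploratory Aim 2, and skin irritation is on the plan's own list of expected events. A participant who has completed twelve weeks could therefore lose the tissue outcomes of Aims 1 and 2 because of a skin reaction to an exploratory device.

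The medication rule raises a different question. It acts after randomisation, and the plan expects TRE to lower blood pressure, atherogenic lipoproteins and glucose. The need to change treatment may therefore differ between arms, and dropping those participants could disturb the balance that randomisation created.

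**Working it through.** **Inputs.** From the power calculation in section 9: 120 enrolled, 15% attrition, 102 completers (51 per arm), independent-samples t-test, significance level 0.05, effect size 0.7. Sidedness is not stated, so two-sided is assumed. The documents give no withdrawal rate by cause, so every count below is an assumption.

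**1. The plan's own figures.** Attrition: 120 × (1 − 0.15) = 102, which reproduces. Power: with 51 per arm the noncentrality is 0.7 × √(51/2) = 3.53 on 100 degrees of freedom, which gives 93.8%, not the stated 80%. The effect detectable with 80% power at 102 is 0.560. This discrepancy is on the safe side and the present point does not depend on it.

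**2. Which withdrawals cost randomised data.**

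- First CGM wear: placed at visit 1, during the two-week screening before randomisation. Removal then costs no randomised data.
- Second CGM wear: placed at visit 4 (week 12) and worn until visit 5 (week 14). Removal then costs visit 5 data, at most two weeks away.
- Blood-draw and biopsy events at visits 2 and 3: can cost visit 5 data. Events at visit 5 lose nothing already collected.
- Medication changes: can cost visit 5 data at any time in the intervention period.

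**3. Precision.** The change in standard error relative to 102 completers is √(102/n) − 1. Detectable effect and power come from the two-sided t-test with equal arms. The rows above 102 assume that 1, 3 or 6 of the 120 − 102 = 18 planned losses attend visit 5 after all. The rows below assume 3 or 6 losses on top of the allowance.

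| n | SE change | Effect detectable, 80% power | Power at 0.5 (example) | Power at 0.7 (planned) |
|---|---|---|---|---|
| 96 | +3.1% | 0.578 | 67.9% | 92.4% |
| 99 | +1.5% | 0.569 | 69.2% | – |
| 102 | 0 | 0.560 | 70.6% | 93.8% |
| 103 | −0.5% | 0.557 | 71.0% | – |
| 105 | −1.4% | 0.552 | 71.8% | – |
| 108 | −2.8% | 0.544 | 73.1% | 95.0% |

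Power at 0.7 falls to 80% only at about 45% attrition: 120 × 0.55 = 66 completers.

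**4. Second CGM wear alone.** If 1%, 3% or 5% of 102 wearers found the symptoms unacceptable, 1.0, 3.1 or 5.1 visit 5 assessments would be lost. Since 102 is already net of attrition, the number wearing the device at visit 4 could be somewhat higher. At the ceiling of 120 the figures are 1.2, 3.6 and 6.0. The percentages are illustrative.

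**5. Direction of any bias.** Control participants might more often need treatment stepped up, or TRE participants might more often need it stepped down. The medication entry allows for both, "including symptomatic high or low blood pressures and symptomatic high or low blood sugars". Nothing in the documents fixes the sign or the size, so no bias figure is given.

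**The case against.** The strongest case against has four parts.

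**The effect is small and already budgeted.** This stands. The plan allows for 15% attrition, and nothing shows that these rules would push losses beyond it. A reader might infer a threat to the trial's power; the table does not support that.

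**The procedure rules are narrower than they look.** This also stands. A reader might infer that any blood-draw or biopsy event, even brief pain, forces withdrawal. But the sentence follows a clause about events arising after the appointment that are referred for medical attention. The closing paragraph of AE Management also speaks of the investigator deciding to discontinue after a serious event. After a biopsy event, a further biopsy may be unwise or refused, so the tissue outcomes may not be recoverable.

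**The CGM case is confined to one wear.** This stands in part. People who cannot tolerate the sensor may leave in the first wear, before randomisation, which would lower the rate in the second. The rule still applies to those who remain. Nor should the actigraphy entry be read as a rule that keeps people in: it asks for notification and does not say what follows. Reapplication concerns a sensor that fell off or failed to record, not a skin reaction.

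**The medication rule is deliberate.** The plan gives its reason, and whether values after a change belong in the main or a supporting analysis is partly a choice of estimand. That is an argument about analysis. It does not require leaving the values uncollected, and collecting them keeps both analyses open.

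Finally, no sentence forbids a visit 5 assessment after withdrawal, and the consent form is not among the documents read. The loss is inferred from removal or withdrawal from the study with only medical monitoring afterwards. If the intention is otherwise, one sentence would settle it.

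**Conclusion.** The point holds as a minor, cheap improvement. The CGM rule expressly ends study participation and not just device wear, and the medication rule does the same. As written, visit 5 values needed by the main regressions would be missing for those affected after randomisation.

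The expected cost is a small loss of precision: about 0.5% to 2.8% in the standard error for 1 to 6 people. It rests on assumed counts, a two-sided t-test and equal arms. Power at the planned effect stays at 92.4% even with six extra losses.

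Medication-change withdrawals add a possible imbalance between arms. A reader might go further and infer bias in favour of TRE. The documents do not support a direction or a size, and procedure and device losses should be similar in the two arms.

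**What to change.** 1. In the CGM entry, state that the sensor is removed and the participant stays in the study.
2. In the blood-draw, CGM, biopsy and medication entries, and in section 14, item 11, state that an adverse event or medication change does not end outcome follow-up. Clinical decisions stay with the investigator. The request to keep doses stable can remain, with a breach recorded.
3. Unless consent is withdrawn or the investigator judges it unsafe, invite these participants to the scheduled visit 5 for the measurements they accept. After a biopsy event this may be only blood, DEXA and anthropometry.
4. Record the date and type of any medication change. In the Statistical analysis text, state that participants are analysed as randomised, and report results with and without values after a medication change.

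The cost is wording in the protocol and analysis section, a few more attendances at a visit already scheduled, and some medication-affected values in one of the two analyses. No new procedure or assay is needed.

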### **Plan for data management**

Data will be collected using standardized paper forms and will only be identified with the study's ID of the participant. The codes that link the name of the participant and the study ID will be kept confidential by the Principal Investigator in a secured cabinet. Data will be entered in the computer independently by UCSD certificated and trained data entry staff, and discrepancies corrected by a supervisor based on source documents.

mCC app: To avoid losing or publicly exposing any collected data on the server, data will be backed up in a separate back-up cloud server. This system uses multiply redundant hardware and software strategies to protect against data loss. By design, the filenames include a randomly generated string, date and time in the filename making it virtually impossible to guess a particular filename. We use the geolocation data for additional utility will be used to evaluate the individual's daily eating, activity pattern associated with access to healthy food, public park, etc. In addition, we shall specifically advise the subject regarding limits imposed by certain wireless carriers (e.g. AT&T) on data uploads, as well as the fact that depending on their device settings the location at which a food photo is clicked may be included in the EXIF information for the JPEG file transmitted to our servers.

Data quality will be monitored by random inspection of the completed forms by the PI. If necessary, re-training of data collectors will be conducted.

### **16. PRIVACY AND CONFIDENTIALITY CONSIDERATIONS INCLUDING DATA ACCESS AND MANAGEMENT**

All study forms including consents, HIPAAs, and case report forms (CRFs), which will include elements from the present and past history, patient demographics, including age, current medications and lab draws, will be stored in a locked cabinet in [name] office in the ACTRI building. Only approved study personnel will have access to this

information. To minimize the potential loss of confidentiality, patients will be assigned a unique number as their subject identifier code. The unique subject code will be used to label all study documents.

Some portions of the specimens collected may be sent to a central laboratory outside of UCSD for testing. All samples will be labeled with a unique specimen code and the only way to link the specimens with the subject code and any personal health identifiers will be on a physical sheet of paper locked in a cabinet in [name] office in the ACTRI building.

Social security numbers will be collected only for purposes of subject payment. This information will only be available to study personnel and will be secured in the same manner mentioned above.

